Post Marketing Surveillance Study - Retrospective Study Endofast Reliant SCP Protocol

Document No.

CL-SCP-60-04

Revision

00

Page

1 of 2

Post Marketing Clinical Follow Up (PMCF) Study

A Retrospective Study for collecting data on
the Safety and Performance of the EndoFast Reliant SCP in
Vaginal Wall Reinforcement
Study Protocol

March 13, 2017

Study Synopsis

| | |
|----------------------------------|---|
| Study Design | A Single arm, single site, retrospective cohort Post Marketing Surveillance Study Evaluating the Safety and Performance of the EndoFast Reliant SCP for apical support |
| Study device: | EndoFast Reliant SCP |
| Intended use: | The EndoFast Reliant SCP is indicated for fixation of surgical mesh to tissue for tissue reinforcement during laparotomy or laparoscopic Sacrocolpopexy approach. |
| Device Regulatory status: | CE, AMAR and FDA Approval |
| Objective: | The objective of this study is to collect data on the anatomical cure and safety of the EndoFast Reliant SCP |
| Medical Centers | One site in Germany Catholic Hospital Hoxter, Germany [name] |
| Population: | Female subjects >18 years old that underwent Pelvic Organ Prolapse repair utilizing the EndoFast Reliant SCP |
| Procedure: | Pelvic Organ Prolapse repair utilizing the EndoFast Reliant SCP |
| Follow-up: | Upon availability of the data (retrospective study) |
| Safety Endpoint: | The safety endpoint counts the rate of peri and post-operative device related Adverse Events. |
| Effectiveness Endpoints: | measures the relative improvement in Pelvic Organ Prolapse staging using the POPQ grading system |
| Inclusion criteria | All Female subjects >18 years old that underwent Pelvic Organ Prolapse repair utilizing the EndoFast Reliant SCP |
| Exclusion criteria | Patients without follow-up |
| Sponsor: | IBI, Israel Biomedical Innovations Ltd. [name] [contact] [contact] |

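### Women without follow-up are excluded from the whole study, so even the peri-operative event rate depends on returning; secondarily, neither endpoint names a reference time

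*Protocol*

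**What the plan says.** All the relevant text is in the Study Synopsis of the protocol.

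- Study Design: "A Single arm, single site, retrospective cohort Post Marketing Surveillance Study". There is no comparator.
- Inclusion criteria: "All Female subjects >18 years old that underwent Pelvic Organ Prolapse repair utilizing the" study device.
- Exclusion criteria: "Patients without follow-up". This is the only exclusion. It is not limited to any endpoint, and no minimum follow-up is defined.
- Safety Endpoint: "The safety endpoint counts the rate of peri and post-operative device related Adverse Events". Two phases are named and neither is bounded in time.
- Effectiveness Endpoints: "measures the relative improvement in Pelvic Organ Prolapse staging using the POPQ grading system". No assessment time is given.
- Follow-up: "Upon availability of the data (retrospective study".

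**The concern.** The main problem is a mismatch between the exclusion and the first half of the safety endpoint. Peri-operative events happen during the operation and hospital stay, and observing them needs no later visit. A woman who was treated and discharged and never returned has a known peri-operative outcome, or should have one in her chart. The exclusion row nevertheless takes her out of both numerator and denominator. What is then reported is the peri-operative rate among women who came back, not among women treated. Whether a woman returns may depend on how the operation went: one with a complication may be more likely to be seen again, or may be referred elsewhere and lost. The direction cannot be predicted.

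The secondary problem is timing. Any length of follow-up is accepted and neither endpoint names a reference time. The post-operative rate and the POPQ improvement may therefore mix observations made at different times after surgery. In a single-arm study no comparator shares that mix, so a crude event proportion could move with the length of follow-up while the underlying risk stays the same.

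**Working it through.** The protocol states no sample size, event rate or follow-up length, so there is no figure to reproduce. The textual check carries the point. The arithmetic only shows what the wording permits, and every input in it is assumed.

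**1. The rows side by side.** Inclusion takes all treated women. Exclusion removes those without follow-up, with no endpoint exempted. The Safety Endpoint row covers the peri-operative phase. Together they give a peri-operative rate computed only in women with follow-up.

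**2. What the exclusion could do.** Let s be the share of treated women excluded, p_f the peri-operative rate in followed women (the one reported) and p_n the rate in excluded women.

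Rate in all treated women = (1 − s)·p_f + s·p_n

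Assume p_f = 3%:

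| s | p_n = 1% | p_n = 3% | p_n = 10% |
|---|---|---|---|
| 5% | 0.95×3 + 0.05×1 = 2.9% | 3.0% | 0.95×3 + 0.05×10 = 3.35% |
| 30% | 0.70×3 + 0.30×1 = 2.4% | 3.0% | 0.70×3 + 0.30×10 = 5.1% |

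The reported figure is 3.0% in every cell. It is right only if the excluded women have the same risk.

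**3. What the follow-up mix could do to a crude proportion.** Assume a 12-month risk of 10%, with women followed for either 1.5 or 24 months. Let p0 be the part of that risk that is peri-operative, and let the hazard be constant afterwards.

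h = −ln(0.9/(1 − p0))/12 per month; risk by t = 1 − (1 − p0)·exp(−h·t)

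- p0 = 0: the risk is 1.31% by 1.5 months and 19.0% by 24 months. With 70% short and 30% long, 0.7×1.31 + 0.3×19.0 = 6.6%. With the shares swapped, 0.3×1.31 + 0.7×19.0 = 13.7%.
- p0 = 5% (half the 12-month risk): the risks are 5.64% and 14.74%. The mixes give 0.7×5.64 + 0.3×14.74 = 8.4% and 0.3×5.64 + 0.7×14.74 = 12.0%.

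The spread falls from 7.1 to 3.6 points when half the risk is peri-operative.

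**4. Would one pooled rate per patient-year cure this?** Only if the hazard is constant. Expected time at risk per woman is (1 − p0)·(1 − exp(−h·t))/(12h) years.

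- p0 = 0: 0.124 and 1.803 years. The rate is 0.105 per patient-year in both mixes.
- p0 = 5%: 0.118 and 1.801 years. With 70% short, 0.0837/(0.7×0.118 + 0.3×1.801) = 0.0837/0.623 = 0.134. With 30% short, 0.1201/(0.3×0.118 + 0.7×1.801) = 0.1201/1.296 = 0.093.

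With peri-operative events included, the pooled rate still depends on the mix.

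**5. Price of a 12-month estimate.** Assume 100 women, p0 = 0 and censoring unrelated to risk. The standard error of the 12-month cumulative incidence is 0.9·√[(e^{1.5h} − 1)/100 + (e^{12h} − e^{1.5h})/(100 × share followed 24 months)]. This is 5.2 points when 30% are followed for 24 months and 3.5 points when 70% are. The crude proportion has √(p(1 − p)/100) = 2.5 and 3.4 points, but for a quantity tied to no defined time.

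**The case against.** A chart review cannot impose visits, and the Follow-up row says so openly. The objective is to collect data, and the protocol sets no hypothesis or performance threshold that a shifted rate could tip. Narrowing an inclusive criterion by an exclusion row is ordinary drafting. Follow-up is not defined, the number of women affected is unknown, and nothing suggests that their risk differs. Visit windows, the choice among several POPQ records and the estimator usually belong in an SAP, which may exist.

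Much of this stands. Variable follow-up is no error, and the details of windows, record selection and estimator are not raised here. A reader might infer that the plan prescribes pooling of unequal follow-up, that its rate is a crude proportion, or that the POPQ record will be chosen after the charts are seen. The document supports none of these. It does not define the rate, does not rule out reporting by follow-up length, and does not show that any woman has several POPQ records. Nor does it contradict itself by including all treated women and then excluding some.

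The exclusion remains. It is a rule that the protocol itself fixes, and it covers an outcome that needs no follow-up visit. A retrospective design does not require it, because the operative and discharge records already exist.

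**Conclusion.** The point holds for the exclusion. As written, the peri-operative device-related event rate describes women who returned, not women treated. The bias may go either way and is nil if the two groups have equal risk. This assumes that some treated women have a surgical and discharge record but nothing later, and that peri-operative events are recorded there.

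The timing point holds in a weaker form. With no reference time in either endpoint row, results may combine different observation times, and a crude rate could then vary with the follow-up mix. That such mixing will occur, or by how much, cannot be read from the document.

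Confidence is high for what the text says and low for the size of either effect. Descriptive tabulation remains possible, so this is a change that should be made rather than one on which the study stands or falls.

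**What to change.** Before charts are abstracted:

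1. Restrict the no-follow-up exclusion to the POPQ and later-safety analyses. Report peri-operative device-related events up to discharge for all treated women, and state how many had no follow-up.
2. Report post-discharge device-related events separately from peri-operative ones, as cumulative incidence at stated reference times with women censored at last contact. Do not use a single pooled per-patient-year rate. Name a reference time for the POPQ endpoint. Leave windows, record selection and estimator details to the SAP.
3. Report the distribution of follow-up.

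The cost is a few lines of protocol text, plus abstracting discharge, event and last-contact dates, including from charts that hold little else. Fewer women inform later times, so intervals there widen, as the standard errors above illustrate. If women return because of symptoms, censoring is informative; these changes disclose that problem but do not correct it.

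### The study-wide exclusion of women without follow-up makes the peri-operative safety count depend on something that happens after surgery

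*Protocol*

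**What the plan says.** All the relevant text is in the Study Synopsis of the protocol.

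- **Study Design:** "A Single arm, single site, retrospective cohort Post Marketing Surveillance Study".
- **Objective:** "The objective of this study is to collect data on the anatomical cure and safety of the" device. Safety is therefore one of two stated aims.
- **Inclusion criteria:** "All Female subjects >18 years old that underwent Pelvic Organ Prolapse repair utilizing the" device. Every treated adult woman qualifies.
- **Exclusion criteria:** "Patients without follow-up". This is the only exclusion, and it is not tied to any one endpoint.
- **Safety Endpoint:** "The safety endpoint counts the rate of peri and post-operative device related Adverse Events". The two periods are combined in one rate.
- **Follow-up:** described only by whether data happen to be available. No visit, time point or minimum duration is given, and the row does not say whether the inpatient post-operative record counts.

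Nothing in the synopsis keeps women without follow-up for the peri-operative count.

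**The concern.** A peri-operative event has happened, or not, before anyone knows whether the woman will have follow-up. Making follow-up a condition of entry selects patients on a later fact and removes them from both numerator and denominator of an outcome that is already complete in their charts.

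The restriction is reasonable for POPQ change and for later adverse events, since neither can be assessed without post-operative data. That part is not challenged. The difficulty is that one eligibility rule is applied to outcomes with different data needs.

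What is at stake is the peri-operative half of the safety result. Women with a device problem at surgery might return less often, for instance because they went elsewhere for care, or more often, because they were watched more closely. The retained patients cannot show which. The protocol also does not ask for a count of women excluded for this reason, so a reader could not judge how much it matters.

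**Working it through.** The protocol states no sample size, event rate or share without follow-up, so there is no figure of its own to reproduce. The calculation below is an illustration, and **every numerical input is an assumption**.

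**Inputs**

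- p: true peri-operative device-related event rate among all treated women, taken as 2%, 5% or 10%.
- q0: share of event-free women without follow-up, taken as 1%, 5%, 10% or 20%.
- r: how many times as often women with an event lack follow-up, taken as 0.5, 1 or 2. Their share without follow-up is then q1 = r × q0.

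**Formula**

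Reported rate = p(1 − q1) / [p(1 − q1) + (1 − p)(1 − q0)].

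**One case in full.** With p = 5%, q0 = 10% and r = 2, q1 = 20%. The numerator is 0.05 × 0.80 = 0.040. The event-free women retained are 0.95 × 0.90 = 0.855. The reported rate is 0.040 / 0.895 = 4.47%, against a true 5.00%. With r = 0.5, q1 = 5% and the result is 0.0475 / (0.0475 + 0.855) = 5.26%.

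**Reported rate when the true rate is 5%**

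| q0 | r = 0.5 | r = 1 | r = 2 |
|---|---|---|---|
| 1% | 5.02% | 5.00% | 4.95% |
| 5% | 5.12% | 5.00% | 4.75% |
| 10% | 5.26% | 5.00% | 4.47% |
| 20% | 5.59% | 5.00% | 3.80% |

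**Ratio of reported to true rate, over p = 2% to 10%**

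| q0 | r = 2 | r = 0.5 |
|---|---|---|
| 5% | 0.948 to 0.952 | 1.024 to 1.026 |
| 10% | 0.891 to 0.899 | 1.050 to 1.054 |
| 20% | 0.754 to 0.769 | 1.111 to 1.122 |

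At q0 = 1% the ratio runs from 0.99 to 1.005 across r = 0.5 to 2. It is exactly 1 if nobody is excluded or if r = 1.

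**Cross-check from the other side.** Let f be the share of treated women excluded and k the event rate in excluded women divided by that in retained women. Reported rate / all-treated rate = 1 / (1 − f + fk). With f = 20% and k = 2 this is 1 / 1.20 = 0.83, so a reported 5.0% would stand for 6.0% in all treated women. With k = 0.5 it is 1 / 0.90 = 1.11, so a reported 5.0% would stand for 4.5%. The bias again vanishes only if f = 0 or k = 1.

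**Why a single all-treated denominator is not the answer.** If women without follow-up were kept in the denominator for later events, and their true rate were the same as in the others, the post-operative rate would be multiplied by 1 minus the share without follow-up: 0.95, 0.90 or 0.80 at 5%, 10% or 20%. Unobserved time would be counted as event-free. The two periods need different denominators.

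**The case against.** The strongest reply is that harm arises under only one reading. The Follow-up row says "Upon availability of the data (retrospective study)", which can cover any post-operative record, including the inpatient one. On that reading hardly anyone is excluded and the bias is negligible. This stands, and it limits the confidence in the point. But the protocol does not settle the reading, so the site could apply the stricter one. Under the broad reading the exclusion removes almost nobody, and deleting it costs almost nothing.

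A second reply is that denominators and separate reporting belong in the analysis plan, which is not shown, and that charts at a single site can be reopened. It is true that the records are not lost. But this is an eligibility rule, not an analysis set, so a plan working on the collected cohort would not recover women who were never abstracted. Abstracting them later would mean going against the protocol or amending it.

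A third reply is that a combined rate with one denominator needs follow-up for all, so splitting it is a design preference, and that the study sets no hypothesis or threshold for a shifted rate to breach. The first part is fair: this is a better design choice, not a repair of an arithmetical error. The second part limits the consequences but does not remove a possible bias from a stated aim of the study.

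Finally, the shifts are modest beside sampling error. With an assumed 5 events in 100 women, the exact 95% interval is about 1.6% to 11.3%. That is correct, but the interval does not reflect selection, and a larger cohort would narrow it without reducing the bias.

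**Conclusion.** The concern holds. The peri-operative part of the safety endpoint is conditioned on a post-operative fact that it does not need, and the rule sits where a later analysis cannot easily undo it. Neither the direction nor the size of any bias can be fixed from the protocol. Under the assumed inputs the reported rate is 0.95 to 1.03 times the true rate at 5% of event-free women without follow-up, 0.89 to 1.05 at 10% and 0.75 to 1.12 at 20%. The lowest figure requires 40% of women with an event to lack follow-up, and nothing in the protocol supports or excludes that. If inpatient records count as follow-up, the effect could be close to zero. It should be fixed because the remedy is cheap and sound under either reading; confidence that it matters in practice is medium.

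**What to change.** Delete the follow-up condition from the Exclusion criteria row and add a line on denominators:

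- Report peri-operative device-related events separately, with all women treated with the device as the denominator.
- Restrict only the POPQ analysis and the later post-operative event analysis to women with the post-operative data each requires, and say which records qualify, including whether the inpatient record does.
- Report how many treated women lack such data.

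The cost is one reworded row, one added line, abstraction of the operative and inpatient charts of the otherwise excluded women at the single site, and two safety denominators instead of one.
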